12. STATISTICAL CONSIDERATIONS

12a. Sample Size Considerations

For the Aim 2 RCT, we based our sample size and power calculations on the primary outcome of retention in care, obtained from EMR data. This outcome is binary on the individual level. We used the methods described by Hussey and Hughes [32] to determine power assuming an evaluation with 24 clusters and 5 time points (including baseline). We include 24 clinics in this study to account for the possibility that 15% drop-out without replacement. We assumed that only a small proportion of the 40 HIV-positive adolescents enrolled in HIV care per clinic may be newly enrolled or recently re-engaged in care. As such, we estimated the minimum number of records per clinic for 80% power to detect a 15% difference between control and intervention periods. We assumed a coefficient of variation (τ/μ) of 0.25 and calculated the power for a two-tailed test with α =0.05. Based on relevant published data [7], we assumed that 75% of adolescents in the control period will return to clinic after first visit. Under these assumptions, we estimate needing at least 5 adolescents per clinic. As such, the lower bound of the sample size required is estimated to be 720 clinic records (6 records/site X 24 sites X 5time points). If N=20

clinics are retained, we would need 7 adolescents per site, per time point, or a minimum of 700 records total.

In the optimal scenario with an average of 40 adolescents in care at each facility, our estimated analysis sample size would be at least 4,800 (5 time points). Under the same assumptions described above, we would have >99% power to detect a 15% difference in retention between the intervention and control periods.

We expect to have adequate power to detect an intervention effect for the analysis with a broader definition of retention in care (return for any follow-up visit within 6 months), because this is likely a more common pattern of follow-up than either return among newly enrolled or return after re-engagement in care.

12b. Planned interim analyses (if applicable)

Because this is a randomized trial with a stepped-wedge (staggered roll-out) design, there will be no interim analyses or stopping rules.

12c. Overview of analysis plan

Pilot phase

Qualitative feedback from participants, actors, and faculty experts will be used to finalize the case scripts, actor checklist, and HCW satisfaction survey.

Data from the completed faculty checklists will be used to establish competency scores. Participants, faculty experts, and actors will be asked to provide qualitative feedback on the checklist indicators. Inter-rater reliability of the faculty checklist will be determined using Cohen's kappa. We will assess correlation of checklist variables and utilize principal component analysis to reduce the number of variables, using a scree test method to plot eigenvalues. Pass/fail cutoff scores will utilize relative and absolute standard-setting processes [33]. In relative processes, initial pass/fail determinations will depend on the performance of the cohort, such that all scoring less than 1 standard deviation below the mean receives a fail. Relative standards are useful with new trainings where there is no prior performance data. Subsequently we will explore standard-setting using an iterative combination of the Angoff item-based method and the Hofstee whole-test method. The Angoff method establishes the probability of a borderline student to accomplish each item on the checklist. The sum of probabilities across items is then equal to a passing score. A team review process is convened in which reviewers discuss outlier ratings, assess performance data after pilot testing, and revision of ratings if necessary. The Hofstee whole-test method combines normative and absolute judgments, in that checklist reviewers make four determinations: the minimum and maximum acceptable passing scores. and the minimum and maximum proportions of students failing. A final cut-off determination will be made by averaging the Hofstee and Angoff scores.

Stepped-Wedge Randomized Controlled Trial

The primary analysis will be an intent-to-treat (ITT) analysis, assuming that adolescents who receive care at clinics after the SPEED training will be 'exposed' to HCWs trained in the SPEED intervention until the end of the study.

A CONSORT diagram, adapted for a stepped-wedge design [34] will be used to show the number of HCW-participants within clusters and flow of randomized stepped wedge clusters though the five time periods. We will report the number of clinics selected for inclusion, assignment to intervention or control at each time period, and the number of HCWs trained at each facility. We will report number of excluded clusters and any reasons for exclusion. No replacement will be used. Facility-specific information – adolescent patient volume, number of HCWs and presence of any adolescent-specific service (peer groups, clinics etc.) prior to the intervention – will be grouped by clinic and recorded. Baseline values of primary and process outcomes, and socio-demographic characteristics of adolescents and HCWs will be presented in a descriptive table.

We will use generalized linear mixed models (GLMM), which are more efficient than paired ttests and linear mixed models (LMMs) in the analysis of cluster RCTs when the size of clusters is unequal [32] to compare the probability of an adolescent returning to clinic after enrollment visit OR second visit after >3 months LTFU between the intervention and control periods [35]. To estimate the effect of the intervention (*Xij*) on the individual level, we will use a GLMM model with a Poisson distribution and robust standard errors, allowing for random effects for clusters (*ui*) and fixed effects for time (*j*). This approach models individual level outcomes, adjusts for temporal trends and accounts for correlation of outcomes within a cluster (clinic). We will estimate adjusted risk ratios (ARR), adjusted risk differences (ARDs) and 95% confidence intervals at the 5% significance level (two-sided). Adjusted risk ratios will be estimated for secondary outcomes: initiating and adherent to ART (≥80% in the dosing period by pharmacy records), 12-month retention in care; viral suppression (<100 copies/ml, <1000 copies/ml), and referred for ancillary services (family planning and TB screening). Models will be adjusted for facility type, patient volume, and exposure to prior adolescent health interventions (c).

The equation for a generic model is: $Y_{ijk} = \beta_0 + \beta j_{time} + \beta_{effect} X_{ij} + \beta c X ij$, $ui + \varepsilon ij$

- Analyses of process outcomes to understand intervention mechanisms will include:
 - Mean HCW competency (passing score proportion per clinic) before and after the intervention
 - Association between mean HCW competency scores per facility and adolescent satisfaction scores
 - Associations between mean adolescent satisfaction scores and 1) retention in care (binary), 2) referral to APS services (binary), 3) ART adherence (binary or mean percent), and 4) viral suppression (binary) comparing the exposed and unexposed periods.
- Evaluation of temporal trends: Temporal trends that change over time (e.g. introduction of new HIV treatment guidelines, COVID-19) and potentially impact study outcomes can lead to a biased effect estimate in a stepped-wedge trial design [34]. To assess this possibility, we will repeat the primary analyses including an interaction term between a time indicator (e.g. coded as 'pre' versus 'post' policy/program change) and the variable for the main effect. A p-value for the interaction <0.1 will be evidence of interaction. We will report these results in a separate table showing any differences in intervention effect by this temporal change.

- Lag effects of SPEED intervention: Because the effect of the intervention may not be immediate or it may diminish over time, we will evaluate these possibilities in two ways. HCWs may take time to put skills they learned in the training into practice. In addition, trained HCWs may decrease or stop using these new skills. Intervention lag will be modeled by re-coding the first month after the intervention as a control period, as recommended by Davey *et al.* [34]. We will model the reduction of the intervention effect over time by using a fractional term for the coefficient of primary effect estimate, which will have a value of 1 (assumes 100% exposure) and get smaller at each time step (e.g. 75%, 50%, 25%).
- Qualitative analysis of exit interviews: Qualitative data from the HCW exit interviews will be coded in Atlas.ti. Data will be analyzed by two reviewers using thematic analysis according to the interview guide. These results will be utilized to complement results from the structured HCW satisfaction surveys.

Cost-effectiveness Analysis (CEA) and Cost Utility Analysis (CUA)

We will develop a cost-effectiveness analysis (CEA) and mathematical model to determine costeffectiveness of the SP intervention. Costing data will be sourced from actual study costs using local rates, as well as primary data collection from adolescents supplemented by published literature to estimate direct medical costs, direct non-medical costs and indirect costs. Direct costs include laboratory tests, and personnel. Direct non-medical costs include transportation costs and field allowances. We will estimate the cost-effectiveness of the SP intervention in terms of cost per additional HIV-infected adolescent identified and retained in care.

We will also model the cost-utility of the intervention in terms of cost per life year saved and disability-adjusted life year (DALY) averted by maintaining HIV-infected adolescents in care, including subsequent decreases in HIV transmission/acquisition.

We will examine how these estimates vary through one-way and probabilistic sensitivity analyses in settings with varying adolescent HIV prevalence, health care HCW wages, population density, and linkage to care rate; identifying scenarios where the intervention is most cost-effective, allowing policymakers to determine incremental costs and net benefits of the intervention. Analyses will be performed both from the programmatic perspective of the Kenyan government and from the societal perspective. All benefits and costs will be discounted at 3% per year.

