8. STUDY SCHEDULE

In this trial, there will be 4 waves of 6 clinics per wave, and 5 measurement periods, including baseline (Table 3). Total duration of the trial is approximately 3 years. Each wave will be rolled out approximately every nine months. Data pulls will occur 15 months after the HCW training, to ensure that all clients who present within the exposure time period have a full 6 months to return for care.

	Introduction of Intervention									
Clinic clusters	Baseline	Month 1	Month 10	Month 19	Month 28					
Wave 1: Sites 1-6	0	Х	Х	Х	Х					
Wave 2: Sites 7-12	0	0	Х	Х	Х					
Wave 3: Sites 13-18	0	0	0	Х	Х					
Wave 4: Sites 19-24	0	0	0	0	Х					

An overview of the anticipated overall study schedule for one wave is shown in Table 4, following page. The study will be conducted over five years. During year one, we anticipate script development, recruiting and training SPs, developing measurement checklists, and piloting initial encounters at Kenyatta National Hospital. During year two, we will recruit and randomize study sites, and begin implementation of the intervention. The intervention will be rolled out in waves, completing measurement and intervention cycles during year 4. Year 5 will be dedicated to statistical outcome analyses, cost effectiveness analyses and modeling, and dissemination of study findings both locally and internationally.

SPEED Protocol Protocol # Version 7.0 May 11 2020

Table 4. Overview of SPEED Study 2015 - 2020

	Y1		Y2			Y3			Y4				Y5							
	Q1	Q2	Q3	Q4																
Study Planning		1		I	1		I													
Protocol development																				
IRB Submissions																				
Implementation	r			1	1	ī	r	Ū	ī											
Site selection																				
Actor Training																				
Pilot phase																				
Consents & Randomization																				
Baseline OR EMR data pull					х				х				х				х	х		
Wave 1																				
Training																				
Exposure time & data pull (X)									Х											
Wave 2					Х															
Training																				
Exposure time & data pull (X)												Х								
Wave 3					Х															
Training																				
Exposure time & data pull (X)															Х					
Wave 4					Х															
Training																				
Exposure time & data pull (X)																		Х		
Post-trial data pull																			Х	
Analysis																				
Data Analysis																				
Dissemination	1	1		1			1													

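### Section 12a gives two minimum cell sizes, 5 and 6 per clinic, for the same 24-clinic scenario, and omits the variance inputs needed to tell which one gives 80% power

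*Combined protocol and SAP*

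**What the plan says.** All the figures are in section 12a (Sample Size Considerations) unless noted.

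- Method: "We used the methods described by Hussey and Hughes [32] to determine power", with 24 clinics and 5 time points. Section 8 gives the layout: "there will be 4 waves of 6 clinics per wave, and 5 measurement periods, including baseline".
- Target: the "minimum number of records per clinic for 80% power to detect a 15% difference between control and intervention periods".
- Variation and test: "We assumed a coefficient of variation (τ/μ) of 0.25 and calculated the power for a two-tailed test with α =0.05".
- Control-period return rate: 75%.
- Minimum with 24 clinics: "Under these assumptions, we estimate needing at least 5 adolescents per clinic".
- Lower bound on the total, in the following sentence: "720 clinic records (6 records/site X 24 sites X 5time points").
- If 20 clinics remain: 7 per site per time point, 700 records.
- With 40 adolescents per clinic: at least 4,800 records and more than 99% power.

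Section 12a does not give the within-clinic variance, does not define μ in τ/μ, and does not say whether the 15% difference is absolute or relative.

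**The concern.** The 5 and the 6 are both offered as the per-clinic minimum for one scenario: 24 clinics, 80% power, the same assumptions. The second is introduced as following from the first, but it cannot, because 5 per clinic does not produce 720 records.

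This figure matters more than most lower bounds. Section 12a expects only a small share of each clinic's 40 adolescents to be newly enrolled or re-engaged, and those are the adolescents in the first definition of the primary outcome. The power claim for that definition rests on the minimum cell size. As written, a reader cannot tell whether the floor is 600 or 720 records, and cannot reproduce either one because two inputs are missing.

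**Working it through.** **Totals**

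- 5 x 24 x 5 = 600
- 6 x 24 x 5 = 720 (the stated total)
- 7 x 20 x 5 = 700 (the stated total)
- 40 x 24 x 5 = 4,800 (the stated total)

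The gap is 720 − 600 = 120 records, one per clinic per time point.

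**Inputs for power**

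From the plan: I = 24 clinics, T = 5 periods, 4 waves of 6, control rate 0.75, coefficient of variation 0.25, two-sided α = 0.05.

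Assumed: the 15% difference is absolute, 0.75 to 0.90, so δ = 0.15; equal cell sizes n; and several choices of within-clinic variance s² and of μ in τ = 0.25μ.

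**Formula (Hussey and Hughes)**

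With σ² = s²/n:

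Var = Iσ²(σ² + Tτ²) / [(IU − W)σ² + (U² + ITU − TW − IV)τ²]

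Power = Φ(δ/√Var − 1.96)

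For 24 clinics:

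- U = 6(4+3+2+1) = 60
- W = 6² + 12² + 18² + 24² = 1,080
- V = 6(16+9+4+1) = 180
- IU − W = 1,440 − 1,080 = 360
- U² + ITU − TW − IV = 3,600 + 7,200 − 5,400 − 4,320 = 1,080

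For 20 clinics (waves of 5): U = 50, W = 750, V = 150, and the two bracketed terms are 250 and 750.

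**Reproducing the 6 and the 7**

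Take s² at the mean proportion, 0.825 x 0.175 = 0.144375, and τ = 0.25 x 0.75 = 0.1875 (τ² = 0.035156).

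- 24 clinics, n = 5: σ² = 0.028875. Var = 24(0.028875)(0.028875 + 0.175781) / [360(0.028875) + 1,080(0.035156)] = 0.14183/48.364 = 0.002933. SE = 0.05415, δ/SE = 2.770, power = Φ(0.810) = 79.1%.
- 24 clinics, n = 6: SE = 0.04975, power 85.4%.
- 20 clinics, n = 6: SE = 0.05450, power 78.6%.
- 20 clinics, n = 7: SE = 0.05070, power 84.1%.

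The whole-number minima are 6 and 7, the figures behind 720 and 700. Power at 40 per clinic is above 99%, as stated.

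**Other conventions, same formula**

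| s² | μ for τ | 24 clinics, n=5 | 24 clinics, n=6 | Minimum n, 24 clinics | Minimum n, 20 clinics |
|---|---|---|---|---|---|
| Mean proportion, 0.1444 | 0.75 | 79.1% | 85.4% | 6 | 7 |
| Average of arms, (0.1875+0.09)/2 = 0.1388 | 0.75 | 80.6% | 86.7% | 5 | 6 |
| Average of arms, 0.1388 | 0.825 | 80.0% | 86.3% | 5 | 7 |
| Control minus τ², 0.1875 − 0.0352 = 0.1523 | 0.75 | 77.1% | 83.7% | 6 | 7 |
| Control, 0.75 x 0.25 = 0.1875 | 0.75 | 69.0% | 76.1% | 7 | 9 |

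**Relative reading of 15%**

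0.75 x 1.15 = 0.8625, so δ = 0.1125. With τ = 0.1875, at least 8 per clinic per time point are needed with 24 clinics under every variance choice tried. With the variance at the mean proportion, power at n = 5 is 51.7%. This fits neither 5 nor 6, so the absolute reading is the one consistent with the plan.

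**The case against.** The strongest reply is that 5 may be right and 6 the outlier. With the average of the two arm variances and τ taken from 0.825, 5 per clinic just reaches 80% with 24 clinics (80.05%). With 20 clinics, 6 gives 79.6%, so 7 are needed. That reproduces the stated 5 and the stated 7, and leaves 6 as a cautious figure. The variance at the mean proportion gives 6 and 7 instead. Since section 12a states neither input, its own figures do not single out one convention. This objection stands as far as it goes: the documents do not show which number is the slip. It does not remove the contradiction, because 5 per clinic still cannot give 720.

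Three stronger or alternative readings are tempting, and the documents do not support them.

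- A reader might infer that the trial is underpowered at its stated minimum. At 5 per clinic, the result is 0.9 points below 80% under one ordinary convention and at or just above it under another. Only the full control-arm variance gives a large gap. The total actually carried forward, 720, already uses 6.
- A reader might infer that clinic-periods with 5 records would be accepted as adequate. No section sets such a threshold. Table 2 specifies a complete record audit of up to 50,000 records, and eligible clinics must have at least 40 adolescents in care.
- A reader might explain the 6 as 5 inflated for 15% loss (5/0.85 = 5.9). Section 12a applies the 15% to clinics (24 x 0.85 = 20.4) and handles it through the 20-clinic scenario. It says nothing about inflating records.

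The minimum of 5 adolescents in section 5e concerns the satisfaction survey and does not bear on the retention records.

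**Conclusion.** The contradiction is certain from the text: 5 against 6 per clinic, 600 against 720 records, a difference of 120. Whether 5 reaches 80% power is borderline and depends on inputs the plan does not state: 79.1% with the variance at the mean proportion, 80.0% to 80.6% with averaged arm variances, and 69.0% with the control-arm variance. Six per clinic per time point reaches 80% under every row of the table (83.7% to 86.7%) except the control-arm variance (76.1%).

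These powers assume an absolute effect of 75% to 90%, equal cell sizes, and the Hussey and Hughes model that the plan names. The point is a minor correction to a stated sample-size figure. It does not show a material loss of power.

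**What to change.** In section 12a, make the two sentences agree in one of two ways.

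- Preferred: restate the minimum as 6 adolescents per clinic per time point. This matches the existing 720 total, and the 7 and 700 for 20 clinics follow from the same convention (variance at the mean proportion, τ = 0.1875).
- Otherwise: keep 5, correct the total to 600, and show the convention under which 5 reaches 80%. The 20-clinic figure must then be rechecked under that convention. With averaged arm variances it stays at 7 if μ = 0.825, but becomes 6 (80.1% power, 6 x 20 x 5 = 600 records) if μ = 0.75.

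In either case, state the effect as 75% to 90% in absolute terms, name the within-clinic variance, and define μ.

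The cost is one or two sentences. Under the preferred option the stated minimum becomes slightly less favourable. Clinics, waves, periods and data collection are unchanged.

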1. BACKGROUND INFORMATION AND SCIENTIFIC RATIONALE

1a. Background Information

Sub-Saharan Africa has disproportionately high burden of adolescent HIV infection

Despite enormous expansion of HIV testing and treatment services in resource-limited settings, adolescents (ages 10-19) and youth (ages 20-24) continue to be substantially and disproportionately affected by HIV [1]. In 2012, an estimated 2.1 million adolescents were living with HIV, and 300,000 adolescents were newly infected [2]. And while mortality has decreased in adult and pediatric populations, there has been a 50% *increase* in adolescent HIV-related deaths over the last 7 years. Sub-Saharan Africa is home to 80% of adolescents and youth living with HIV globally [3]. Kenya alone accounts for 7% of all new adolescent HIV infections [2].

Substantial barriers for adolescent linkage to and retention in the HIV care cascade

Although HIV services have expanded throughout Africa, there has been less programmatic focus on adolescent HIV care than on adult care [1, 4, 5]. Inadequate provision of accessible and acceptable HIV testing, counseling, and treatment services is cited as a barrier to uptake of and retention in HIV care among adolescents [6]. For example, a recent Kenyan HIV treatment cohort study reported that 25% of youth and adolescents did not return after their first visit, 41% were lost in the first 12-months of the pre-ART period, and 21% of those initiating ART were lost within one year; rates higher than reported in adult programs [7]. Optimizing impact of HIV treatment programs requires early identification of HIV status, prompt linkage to care, and sustained adherence to antiretroviral therapy (ART). Loss throughout the care cascade translates to poor health outcomes and increased mortality, and subsequent HIV transmission due to uncontrolled viral load in all age groups. There is an urgent need for evidence-based interventions that promote adolescent uptake of and retention in HIV care [5].

HCWs lack confidence in their ability to provide HIV care for adolescents

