An individual who meets any of the following criteria will be excluded from participation in this study: Conditions that would place the individual at increased risk or preclude the individual's full compliance with or completion of the study. This applies both to the pilot phase and the RCT.

Table 2. Inclusion	on Criteria for all P	articipants
--------------------	-----------------------	-------------

Population	Sampling	N	Inclusion Criteria
	Selected from clinics		≥40 adolescents currently in HIV care
Clinic clusters	with ≥40 adolescent clients	24	EMR data system
			No concurrent adolescent interventions
			>18 years of age
Health Care Workers (e.g. doctors, nurses, clinical officers, nurse counselors)	Up to 10 per clinic	240	Employed at trial site in clinical care for at least three months and/or have a 1 year contract (i.e. not temporary staff)
			Provides clinical services to adolescents
Adolescent client records	Complete record audit	Up to 50,000	Records of clients age 10-24 in trial sites
			Ages 10-24
Adolescent clients	escent clients Up to 20 per clinic per time point		Seeking counseling or treatment services at trial site
			HIV-infected

5e. Strategies for recruitment and retention

Pilot phase

Up to 10 HCWs who are >18 years of age, and employed in HIV care at Comprehensive Care Centers (CCCs) and adolescent clinics at KNH will be recruited to participate in the pilot testing of study tools and scoring rubric. We will obtain permission from the clinic directors before recruitment. We will receive a list of potential participants. A member of the study team will be stationed at the clinics and approach potential participants to learn more about the pilot testing phase of the study. In this phase, HCW participants will take part in a pilot 2-3 day training that includes a didactic component, 6-7 SP encounters, group debriefing and discussion. Participants will provide their contact information to ensure completion of the training.

Stepped-wedge randomized controlled trial

Clinics/individual HCW participants: For the stepped-wedge trial, the SPEED study team
will identify up to 24 clinics that meet study eligibility criteria. We will receive permission
from NASCOP and local administrative teams to enroll these clinics. We will then send
letters to administrative teams of the selected clinics. The letter will have information on
the objectives of the SP intervention and will include a formal request for the clinic to be

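### The >99% power figure for 4,800 in-care records rests on a first-visit return rate; no control rate is given for actively enrolled adolescents

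*Combined protocol and SAP*

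**What the plan says.** Section 12a sizes the trial by the Hussey and Hughes method with 24 clinics, 5 time points and a between-clinic coefficient of variation of 0.25. On error rate and target it says that the authors "calculated the power for a two-tailed test with α =0.05" and that "we estimated the minimum number of records per clinic for 80% power to detect a 15% difference between control and intervention periods". The control rate is tied to one kind of visit: "we assumed that 75% of adolescents in the control period will return to clinic after first visit".

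The section expects only a small share of the 40 adolescents per clinic to be newly enrolled or re-engaged, and so arrives at a minimum of 5 to 7 records per clinic per period. It then turns to what it calls the optimal scenario, with all 40 in care counted (at least 4,800 records), and concludes: "Under the same assumptions described above, we would have >99% power to detect a 15% difference in retention between the intervention and control periods".

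For the broader 6-month definition it expects adequate power "because this is likely a more common pattern of follow-up" than return after enrolment or re-engagement. No rate, effect or power figure accompanies that sentence.

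Section 3a has two bullets under the primary outcome: return after an enrolment or re-engagement visit, and any visit within 3 months among those currently enrolled. It describes the second group as neither new nor previously lost. Table 2 sets clinic eligibility at "≥40 adolescents currently in HIV care", and Section 5f puts the median clinic at 73 enrolled.

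**The concern.** The 75% belongs to adolescents at a first visit. The 4,800 records are, by the plan's own account, mostly of adolescents who are past that point. Carrying the same assumptions across attaches a power statement to a population that its control rate does not describe. This can be seen without any assumption about loss rates.

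What is at stake is how a null result would be read. If the active-care analysis showed no effect, a reader would set it against >99% power, although no power was calculated at a control rate chosen for that group. If active clients already return at a high rate, the gains open to them are smaller than 15 points, and power for those gains is a different number.

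**Working it through.** **1. Reproduce the plan's figure.** Inputs from Sections 8 and 12a: 24 clinics in 4 waves of 6, 5 periods, two-sided 5%, control rate p0 = 0.75, τ = 0.25 × 0.75 = 0.1875. The 15% is read as absolute, so p1 = 0.90.

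Hussey and Hughes variance, with s² = σ²/n and σ² the mean of p0(1−p0) and p1(1−p1):

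Var = I s²(s² + Tτ²) / [(IU − W)s² + (U² + ITU − TW − IV)τ²]

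Here I = 24, T = 5, U = 60, W = 1,080 and V = 180, so Var = 24 s²(s² + 5τ²) / (360 s² + 1,080 τ²). Power = Φ(difference/SE − 1.96).

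- σ² = (0.1875 + 0.09)/2 = 0.1388 and τ² = 0.0352.
- n = 5: SE = 0.0532, power 81%.
- n = 6: SE = 0.0488, power 87%.
- n = 40: SE = 0.0195, power above 99.9%.

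The plan's minimum of 5 and its >99% both reproduce. A relative reading of 15% (75% to 86.25%) gives only about 52% at n = 5, so the absolute reading is the one used.

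**2. The ceiling.** p0 + 0.15 ≤ 1 requires p0 ≤ 0.85.

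**3. What the plan's loss figures would imply for active clients.** Section 1a reports that "21% of those initiating ART were lost within one year" and that 41% were lost in the first 12 months before ART. It gives no 3-month rate. Assume, for illustration, constant loss over the year, and that being lost means no visit within 3 months:

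- ART figure: 0.79^(1/4) = 94.3%.
- Pre-ART figure: 0.59^(1/4) = 87.6%.

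Adding 15 points gives 109.3% and 102.6%. The largest possible gains are 5.7 and 12.4 points.

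**4. Does a mixture rescue the 15 points?** With new or re-engaged adolescents at 75% and the rest at 94.3%, the overall rate falls to 85% when the new share is (94.3 − 85)/(94.3 − 75) = 48%. With the rest at 87.6%, it does so at (87.6 − 85)/(87.6 − 75) = 21%. The plan says a small proportion, without a number.

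**5. Power for gains that fit.** Same formula, τ = 0.25 × p0:

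| Control rate | Gain | 40 per clinic-period | 73 per clinic-period |
|---|---|---|---|
| 94.3% | non-return cut by a quarter (to 95.7%) | 23% | 38% |
| 94.3% | non-return halved (to 97.15%) | 77% | 95% |
| 94.3% | +3 points | 81% | 97% |
| 87.6% | +3 points | 45% | 70% |
| 87.6% | +5 points | 89% | 99% |

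A coefficient of variation of 0.25 is not a possible value at 94.3%: τ would be 0.236, above the maximum SD of a proportion with that mean, √(0.943 × 0.057) = 0.232. This matters little. With 0.05 instead, the 40-per-cell results at 94.3% become 79% for halving and 83% for +3 points.

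**The case against.** The strongest reply is that no 3-month retention rate appears anywhere in the documents. The 88 to 94% range needs a constant loss rate, and it needs the cited cohort's meaning of *lost* to match the trial's outcome. The protocol's own definition of loss to follow-up (no record for at least 3 months) makes the match plausible, but the cohort's definition is not given. A client who returns in month 4 fails the trial outcome, yet a cohort might count that client as retained at 12 months; true 3-month return would then be lower than the range suggests. If all of the 21% loss fell in the first quarter, the rate for that quarter would be 79% and a 15-point gain would fit. All of this stands. A reader might infer that the plan's figures put retention at 94% and make a 15-point gain impossible; the documents do not support that as an unconditional statement. Clients past a front-loaded first quarter would, however, have little loss left to prevent.

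A reader might also infer that the trial is underpowered for active clients. That is not shown. The 40 per clinic is the eligibility floor, the plan says at least 4,800, the median clinic has 73, and Table 2 allows an audit of up to 50,000 records. Nor is the >99% a calculation error, since it reproduces.

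The 6-month sentence could be taken as wrong, because a higher control rate leaves less room for an effect. It can equally mean that more clients follow that pattern and so supply more records, and variance also shrinks near 100%. It is unquantified, not shown to be false.

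Finally, the clinic count and the 700 to 720 record minimum come from the enrolment and re-engagement calculation, and the mixed model in Section 12c names that comparison. The design therefore does not rest on the >99% statement. None of this supplies a control rate for the active group.

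**Conclusion.** The point holds as a mismatch between an input and the population it is applied to. Section 12a attaches >99% power for a 15-point difference to 4,800 in-care records using a first-visit rate, and gives no control rate for the actively enrolled, whose 3-month return is listed under the primary outcome. That much rests on the text alone.

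The size is conditional. Under constant loss and a matching definition of loss, the control rate would be roughly 88 to 94% and a 15-point gain unattainable. Power at 40 per clinic-period would then depend heavily on which smaller gain is of interest, and would be higher at realistic clinic sizes. The enrolment and re-engagement calculation is unaffected.

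**What to change.** In Section 12a:

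- Limit the 75% to 90% assumption, and the power derived from it, to enrolment and re-engagement index visits.
- Remove the >99% statement for the 4,800 in-care records.
- State instead the power or detectable difference for active clients at 3 and at 6 months. Use the control rate from the baseline EMR extraction already planned in Section 11, actual clinic volumes, a between-clinic variation that is possible at that rate, and an effect that stays below 100%. The 6-month figure would replace the unquantified sentence.
- Do not enter 94% as the plan's own figure; it is an extrapolation from annual losses.

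The cost is rewording and a short recalculation. Clinics and records do not change. The downside is that the stated power becomes less favourable.
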